8.1. Demographic characteristics

Age (years) and sex will be summarised using descriptive statistics already mentioned.

Age (years) = (reference start date – date of birth) / 365.25 (*rounded at 1 digit*)

8.2. Previous and concomitant medications

Previous and concomitant medications (taken at least once before reference start date) are coded by ATC class and substance name using the WHO-DRUG dictionary version 2022 Q1.

They will be summarised with frequencies and percentages.

Subjects will be counted only once within these ATC categories.

8.3. Medical and surgical past history

Medical and surgical past history is coded using the MedDRA dictionary version 25.0. Diseases are classified by System Organ Class (SOC) and Preferred Term (PT).

The number and percentage of subjects with at least one disease of each category (SOC/PT) will be given.

Subjects will be counted only once within these categories.

8.4. Baseline efficacy variables

Each item of the SNOT-22 and the resulting score will be described at baseline.

The following sub-domains of the SNOT-22 will be described:

- Nasal domain based on items 1-2-3-4-5-6-21-22
- Ear/facial domain based on items 7-8-9-10
- Sleep domain based on items 11-12-13-14
- Function domain based on items 15-16-17
- Emotion domain based on items 18-19-20

8.5. Baseline safety variables

Adverse events since enrolment will be described at baseline.

Serious adverse events potentially related to the sino-nasal swab procedure will be described at baseline.

8.6. Other baseline variables

Sino-nasal symptoms will be described at baseline.
Rhinologic examination will be described at baseline.

9. COMPLIANCE

Compliance will be calculated according to the following formula and analysed on the Safety Set:

$$\text{Compliance (\%)} = \text{Real quantity used (g)} * 100 / \text{Theoretical quantity used (g)}$$

With:

- Initial weight = 199.5 g
- Theoretical weight after 30 days of treatment (g) = 154.5 g
- Theoretical quantity used (g) = $199.5 - 154 = 45$ g
- Real quantity used (g) = $199.5 - \text{Final weight (g)}$

In case of trial spray not returned, compliance will be considered unknown and missing.

Note:

- The analysis of compliance will be purely descriptive.
- Usually, only the global compliance will be estimated.

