4.7 Device Description

Healsea® Chronic is a nasal spray (available in 50 or 150mL) using the Bag-on-Valve (BoV) technology.

The BoV technology consists of an aerosol valve with a welded bag. The product is placed inside the bag while the propellant is filled in the space between bag and can. The product is dispensed by the propellant simply squeezing the bag when the spray button is pressed, the product is squeezed out of the bag by the compressed air/nitrogen, which creates the dispensing as a spray. Therefore, the product keeps its integrity, remaining separated from the propellant at all times. Compared to traditional aerosol spray technology, BoV has several benefits, for manufacturers, consumers and the environment. Packaging description of Healsea® Chronic is reported in Figure 1.

***The Spray Pin:** Packaging element ensuring the delivery of the product in the patient's nose.

***The Actuator:** Pacifica Spray actuator with a flow rate of 8ml/10s pressed enables the Propellant to squeeze the bag to dispense the product through the Spray Pin.

***The Valve assembly:** Packaging element ensuring the link between the bag and the actuator.

The Can: Standard aerosol aluminum can containing the bag and the propellant.

The Product: Hypertonic Seawater solution (2.2%) supplemented with Symbiofilm® (0.02%)

***The Bag:** FDA-approved laminated bag containing the product.

The Propellant: Because of the separation between product and propellant, BoV technology is used with compressed nitrogen filled between the can and the bag.

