8.2 Investigational device and comparator

The investigational device which is Healsea® Chronic (nasal spray; 150 mL presentation) is a CE marked Medical Device. As this is an interventional study, the device will be provided to the patient. No specific labelling is required as the device will be used within its intended use in this post-market clinical investigation.

No comparator is used in this study.

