8.4 Procedures

8.4.1 Study procedures

The study will comprise 2 visits and 1 telephone call.

Visit 1 (V1) – (Day 1): Screening/Inclusion

The investigator will give oral information relative to the study to the participant and answer to all the questions raised by the patient. If he/she agrees to participate in the study, he/she will be asked to sign and date a consent form.

Each screened subject will be assigned a subject identifier number during screening. The subject identifier number will contain the site number (01) and the subject number assigned in numerical order at the screening visit based on chronological order of screening dates (e.g., 01-10 for the 10th subject screened at the Site #01).

The investigator or his/her delegated designee will:

- Record demographic data and medical history and ongoing medication,
- Perform a rhinologic examination,
- Verify that eligibility criteria are fulfilled,
- Proceed with the middle meatus swab collection,
- Detail the questions of the SNOT-22 and record the patient's score,
- Record adverse events if applicable,
- Explain how to collect adverse events/incidents/expected side effects and concomitant medications for reporting at the telephone call/visit,
- Deliver Healsea® Chronic and explain to the patient how to use it.

The patient will be ask to bring back the container at the end of the treatment period.

D1-D30 (at home):

The patient will be instructed to self administer Healsea® Chronic nasal spray twice a day (1 puff, 1-2 sec) in each nostril during 30 days.

D15±3 (at home): Telephone call

The Investigator or his/her delegated designee will call the patient to review patient status and study progress, adverse events/incidents/expected side effects and concomitant treatments.

Visit 2 (V2) – (Day 30 ±5): end of treatment

The investigator or his/her delegated designee will:

- Perform a physical and clinical examination,
- Record the SNOT 22 score in the CRF,
- Proceed with the middle meatus swab collection,
- Report the adverse events/incidents/expected side effects and concomitant medications in the CRF,
- Ask the patient to complete the satisfaction questionnaire and report the result in the CRF,
- Measure compliance to Healsea® Chronic intake.

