11.5 Procedures to maintain and protect subject privacy

Data privacy is ensured through restricted access to the anonymized data located in a dedicated separate database.

11.6 Methods for database locking at the start of analysis and storage upon completion of the clinical investigation

The validated database will be locked upon request of the Data Manager following the completion of all steps required, i.e. resolution of all queries, validation of the coding, data review meeting.

The review process prepared by the clinical research assistant, data manager, study monitor, medical manager and statistician will be concluded during a meeting (Validation Committee) to be attended by at least the following:

- Coordinating investigator,
- Study monitor,
- Sponsor Vigilance representative,
- Study Coordinator,
- Data manager,
- Statistician.

The review is also required for defining the analysis populations and validating the statistical analysis plan.

The meeting will be documented by written and signed minutes that will act as the basis for data processing by the Biometrics Department.

All decisions on the evaluability of the data from each individual subject for the statistical analysis must be made and documented before locking the database.

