4. SAMPLE SIZE

An arbitrary sample of 20 subjects completing the investigation without major protocol deviation has been chosen.

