5. DEFINITION OF THE ANALYSIS SETS

Screened subjects: all subjects who signed an informed consent

Included subjects: all screened subjects who will have been expected to participate in the study.

Safety Set: all subjects who will have used the investigational medical device at least once.

Full Analysis Set (FAS): all subjects from the Safety Set who will have at least one post baseline Sino Nasal Outcome Test-22 (SNOT-22) evaluation.

Per Protocol Set (PP): all subjects from the FAS without any major protocol deviation.

The status of protocol deviations (minor or major) will be validated during the data review meeting.

Any subject not satisfying major entry criteria or for whom post inclusion data are not available will be identified by the Validation Committee during the data review, and could be excluded from the FAS Set in agreement with circumstances exposed in the ICH-E9 §5.2.1.

Safety analysis will be performed on the Safety Set.

Efficacy analysis (except primary efficacy criterion) will be performed on the FAS.

Note: primary efficacy criterion (16S rRNA gene high throughput sequencing) will be analysed separately by a dedicated team specialized in microbiome analysis.

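### The SAP's 45 g compliance denominator conflicts with the protocol's dosing and actuator rate, which imply at least 2.1 times that amount over 30 days

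*SAP*

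**What the plan says.** SAP section 9 defines compliance as the real quantity used divided by the theoretical quantity used, times 100. The container starts at 199.5 g and the plan gives "Theoretical weight after 30 days of treatment (g) = 154.5 g". The next line prints the theoretical quantity as 199.5 - 154 = 45 g. No mass per press, press time or source is given for the 45 g. The section limits compliance to description.

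The protocol gives the figures from which expected use can be worked out. Section 8.4.1 has the patient use the spray "twice a day (1 puff, 1-2 sec) in each nostril during 30 days". Section 4.7 describes a "Pacifica Spray actuator with a flow rate of 8ml/10s" and a product "available in 50 or 150mL". Section 8.2 names the one used here: "nasal spray; 150 mL presentation".

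The score feeds Table 14.3.1.2 (Safety Set) and Listing 16.2.5. Non-compliance with treatment is a major deviation in SAP section 7.2 and Protocol section 13, and neither gives a percentage cut-off.

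**The concern.** A compliance percentage is read against 100%. If the denominator is far below what full adherence would use, 100% no longer means that the regimen was followed. Adherent patients score well above 100%, and a patient who skipped about half the doses looks compliant. Container weight is the only compliance measure the SAP defines, and the visit schedule shows no dosing diary against which to check it. At stake is the description of exposure in one table and one listing.

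**Working it through.** **Inputs.** Initial weight 199.5 g and theoretical 30-day weight 154.5 g (SAP section 9). Actuator rate 8 mL per 10 s (Protocol 4.7). One puff of 1-2 s, two nostrils, twice a day, 30 days (Protocol 8.4.1). Container 150 mL (Protocol 8.2). Two assumptions are mine: the documents give no density, so I take 1.00-1.03 g/mL for a 2.2% saline solution; and the stated rate is taken to apply to short presses.

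**The plan's own figure.** 199.5 - 154.5 = 45.0 g, which agrees with the stated result. The subtraction as printed, 199.5 - 154, gives 45.5 g. The difference is 0.5/45 = 1.1% and looks like a dropped decimal.

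**Expected use from the protocol.**
- Presses: 2 per day x 2 nostrils x 30 days = 120.
- Rate: 8/10 = 0.8 mL/s.
- Volume = 120 x 0.8 x press time.

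| Press time | Volume | Mass at 1.00-1.03 g/mL | Mass / 45 g | Share of doses scoring 100% |
|---|---|---|---|---|
| 1 s | 96 mL | 96.0-98.9 g | 2.13-2.20 | 45/98.9 to 45/96 = 46-47% |
| 1.5 s | 144 mL | 144.0-148.3 g | 3.20-3.30 | 45/148.3 to 45/144 = 30-31% |
| 2 s | 192 mL | 192.0-197.8 g | 4.27-4.39 | 45/197.8 to 45/192 = 23% |

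The 2 s row exceeds one 150 mL container. Emptying one container gives 150/45 = 3.33 to 154.5/45 = 3.43, so with a single container the ratio stops at about 3.3-3.4 and the score at about 333-343%.

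**What 45 g implies.** 45/120 = 0.375 g per press, or 0.364-0.375 mL. At 0.8 mL/s that is 0.46-0.47 s, under half the instructed minimum.

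**Can the gap be closed?**
- Density: at 1 s the solution would have to weigh 45/96 = 0.47 g/mL, which is not possible for salt water.
- Short-press delivery: average output would have to be 53-54% below the stated rate at 1 s (0.364-0.375 mL against 0.8 mL), and 77% below at 2 s (against 1.6 mL).
- One nostril only at 1 s: 60 x 0.8 = 48 mL, or 48.0-49.4 g. That is 7-10% too high and contrary to the instruction.
- No combination of one or two nostrils with 1, 1.5 or 2 s presses over 30 days reaches 45 g.

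**Rescaling.** New score = old score x 45 / new denominator. With a 96 g denominator, for example, 213% becomes 213 x 45/96 = 100%.

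**The case against.** The strongest reply is that the SAP never says the 45 g comes from the actuator rate. The 8 mL per 10 s may describe a sustained press, and the 45 g may rest on a measured mass per puff. Pack size gives this some support. At 0.8 mL/s, four presses a day at 1 s use 3.2 mL, so the 50 mL presentation would last 50/3.2 = 15.6 days (7.8 days at 2 s). A 30-day course of 45 g is 43.7-45 mL, which fits that pack. This stands as a reason not to call 45 g the error, but it does not settle the matter: 96 mL fits the 150 mL container used here, and if 45 g is right, the protocol's rate or press time needs correcting.

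The second reply is that little depends on the score. This largely stands. SAP section 9 makes compliance descriptive, and section 6.3.1 treats all results that way. A reader might infer that under-use becomes undetectable. It does not: the score stays proportional to grams used. At 1 s, a half-dose patient scores about 107-110% against 213-220% for adherent patients, and scores above 200% would be noticed at data review. Only the reading against 100% is distorted.

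A reader might also infer that the Per Protocol set, or the target of "An arbitrary sample of 20 subjects completing the investigation without major protocol deviation has been chosen", is compromised. The documents do not show this. No cut-off ties the percentage to a major deviation, and deviation status is settled at the data review meeting. Nor are efficacy results affected: "Efficacy analysis (except primary efficacy criterion) will be performed on the FAS", the primary analysis population is set separately (SAP section 10.1), and the table list has no outcome table on the Per Protocol set.

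**Conclusion.** The conflict is real and at least twofold: 96-192 mL expected from the protocol against 45 g in the SAP. The ratio is at least 2.1, and at most about 3.3-3.4 with one 150 mL container; a ratio of 4.4 would need more product than that container holds. The result assumes that the stated rate holds for short presses and, for the ratio, a density of 1.00-1.03 g/mL. Density cannot remove the gap. Only a measured short-press delivery less than half the stated rate could.

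The documents do not identify the wrong figure. Two explanations are tempting: that one nostril was counted, or that 45 g is the empty container weight, since 150 x 1.03 = 154.5. Neither is shown. The first misses by 7-10%, and the second works only at the top of the assumed density range (1.00-1.02 g/mL gives 150-153 g).

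If the protocol's figures are right, the percentages in Table 14.3.1.2 and Listing 16.2.5 misstate adherence by a factor of two or more, but they can be recovered from the returned weights. If 45 g is right, the score works as planned. With no planned efficacy estimate affected and any effect on Per Protocol membership only possible, this is a minor point.

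**What to change.** Before compliance is reported:

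1. Establish the basis of 45 g, from manufacturer data or by weighing a container before and after a set number of timed 1 s and 2 s presses.
2. Correct the figure that proves wrong: the denominator in SAP section 9, the rate in Protocol 4.7 or the press time in Protocol 8.4.1.
3. State the press time the denominator assumes, or report compliance against the 1-2 s range. Weight alone cannot separate 120 presses at 1 s from 60 presses at 2 s: both use 96 mL.
4. If 45 g stands, correct 154 to 154.5 in the printed subtraction.
5. If the denominator changes, recompute the scores from the returned weights.

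The cost is a query to the manufacturer or a short bench check, plus a text edit. No new patient data are needed, because returned container weights are already planned for Table 14.2.4. No change to study conduct is proposed: SAP section 12 records a change made after data review, which suggests that dosing was over.

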4.3 Name or number of the model to permit full identification

The test device is named Healsea® Chronic. It is a nasal spray (150ml presentation), hypertonic seawater (2.2%) supplemented with Symbiofilm® (0.02%) identified by the code article: 75012DMMG

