XXXX sino-nasal symptom – End of study	
N	XX
Missing	XX
Yes	XX (XX.X%)
No	XX (XX.X%)
XXXX sino-nasal symptom – Change from baseline	
N	XX
Missing	XX
Improvement	XX (XX.X%)
No change – symptom present	XX (XX.X%)
No change – symptom absent	XX (XX.X%)
Degradation	XX (XX.X%)

Table 14.2.4. Safety - Secondary efficacy criteria – Weight of device [FAS]

Healsea Chronic N=XX	
Returned device	
N	XX
Missing	XX
Yes	XX (XX.X%)
No	XX (XX.X%)
Weight of returned device	
N	XX
Missing	XX
Mean (SD)	XX.X (XX.X)
Median	XX
Q1/Q3	XX / XX
Min/Max	XX / XX

Table 14.3.1.1. Safety - Study duration by subject [Safety Set]

Healsea Chronic N=XX	
Study duration (days)	
N	XX
Missing	XX
Mean (SD)	XX.X (XX.X)
Median	XX
Q1/Q3	XX / XX
Min/Max	XX / XX

Table 14.3.1.2. Safety - Summary of compliance [Safety Set]

Healsea Chronic N=XX	
Compliance (%)	
N	XX
Missing	XX
Mean (SD)	XX.X (XX.X)
Median	XX
Q1/Q3	XX / XX
Min/Max	XX / XX

Table 14.3.1.3. Safety – Concomitant treatments [Safety Set]

ATC1 - ATC2	Healsea Chronic N=XX
Subjects with at least one concomitant treatment	
All	XX (XX.X%)
XXXXXX	
All	XX (XX.X%)
XXXXX	XX (XX.X%)
XXXXX	XX (XX.X%)

Table 14.3.2.1 Safety – Brief summary of incidents related to the use of the medical device [Safety Set]

Number and percentage of subjects with related / Number of related	Healsea Chronic N=XX	
	n (%)	[E]
Incident	XX (XX.X%)	XXX
Incident leading to definitive study device discontinuation	XX (XX.X%)	XXX
Incident leading to definitive study discontinuation	XX (XX.X%)	XXX
Serious incident	XX (XX.X%)	XXX
At least one treatment-emergent incident	XX (XX.X%)	XXX
Exactly one treatment-emergent incident	XX (XX.X%)	XXX
Exactly two treatment-emergent incident	XX (XX.X%)	XXX
At least three treatment-emergent incidents	XX (XX.X%)	XXX

Table 14.3.2.2 Safety – Brief summary of adverse events not related to the use of the medical device [Safety Set]

		Healsea Chronic N=XX	
		n (%)	[E]
Number and percentage of subjects with related / Number of related			
Incident		XX (XX.X%)	XXX
Incident leading to definitive study device discontinuation		XX (XX.X%)	XXX
Incident leading to definitive study discontinuation		XX (XX.X%)	XXX
Serious incident		XX (XX.X%)	XXX
At least one treatment-emergent incident		XX (XX.X%)	XXX
Exactly one treatment-emergent incident		XX (XX.X%)	XXX
Exactly two treatment-emergent incident		XX (XX.X%)	XXX
At least three treatment-emergent incidents		XX (XX.X%)	XXX

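### The SAP's 45 g compliance denominator and the protocol's spray rate and regimen, which imply at least 96 g, cannot both be right

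*SAP*

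**What the plan says.** SAP section 9 defines compliance as the real quantity used divided by a theoretical quantity, times 100. The real quantity is 199.5 g minus the final can weight. The theoretical quantity is a constant for every subject, built from "Theoretical weight after 30 days of treatment (g) = 154.5 g" and then "Theoretical quantity used (g) = $199.5 - 154 = 45$ g". No derivation of 154.5 g from puff size or puff count is given. The section adds: "The analysis of compliance will be purely descriptive". Table 14.3.1.2 summarises the percentage on the Safety Set.

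Protocol section 4.7 describes the "Pacifica Spray actuator with a flow rate of 8ml/10s pressed". Protocol section 8.4.1 tells the patient to "self administer Healsea® Chronic nasal spray twice a day (1 puff, 1-2 sec) in each nostril during 30 days". The synopsis, section 4.1 and the instructions for use give the same regimen. Sections 4.3 and 8.2 both identify the device as the 150 mL presentation.

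**The concern.** The denominator should be what a patient who follows the regimen would use in 30 days. The protocol states the flow rate, puff length, puffs per day and number of days, so that amount can be calculated directly. It comes out at more than twice 45 g, even at the shortest permitted puff.

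This is a single-arm before/after study, so the compliance table is the reader's main evidence that patients received the month of exposure the primary objective assumes. If the scale is wrong, a group that used under half the regimen would be reported as fully compliant, and the microbiome and SNOT-22 changes would be read as the result of complete exposure.

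**Working it through.** **The SAP's own figure.** 199.5 - 154.5 = 45.0 g, so the constant reproduces from the theoretical final weight. The printed subtraction, 199.5 - 154, would give 45.5. The 154 looks like 154.5 with a lost decimal, possibly only in the text copy of the file. Nothing below depends on it.

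**Inputs**
- Flow rate: 8 mL / 10 s = 0.8 mL/s (Protocol 4.7).
- Puffs: 2 nostrils x 2 per day x 30 days = 120 (Protocol 8.4.1).
- Puff length: 1 to 2 s (Protocol 8.4.1).
- Can: 150 mL (Protocol 4.3 and 8.2).
- Density: not stated; assumed 1.00-1.02 g/mL for 2.2% saline.

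**Amount implied by the protocol** = flow rate x seconds per puff x 120 x density
- 1 s: 0.8 x 1 x 120 = 96 mL; x 1.00-1.02 = 96-97.9 g.
- 2 s: 0.8 x 2 x 120 = 192 mL; x 1.00-1.02 = 192-195.8 g. This exceeds the 150 mL can (150-153 g), which would be empty after 150 / 6.4 = 23.4 days.

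**What 45 g implies**
- Per puff: 45 / 120 = 0.375 g. At 0.8 mL/s that is 0.375 / 0.8 = 0.47 s (0.46 s at density 1.02), under half the shortest permitted puff.
- Flow rate needed for 45 g: 3.75 mL per 10 s with 1 s puffs (density 1.00), down to 1.84 mL per 10 s with 2 s puffs (density 1.02). The protocol says 8.

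**Effect on the reported percentage if 0.8 mL/s is right**
- Full adherence at 1 s: 96 / 45 = 213% to 97.9 / 45 = 218%.
- Can emptied: 150 / 45 = 333% to 153 / 45 = 340%.
- A reported 100%: 45 / 96 = 46.9% to 45 / 97.9 = 46.0% of the minimum regimen.
- Days of full use needed to score 100% (density 1.00): 45 / 3.2 = 14.1 at 1 s, or 45 / 6.4 = 7.0 at 2 s.

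**Other readings tried**
- V2 at its earliest, Day 25: 100 puffs x 0.8 = 80 mL at 1 s, still well above 45 g.
- Half the puffs (one nostril only, or once daily): 60 x 0.8 = 48 mL. This is near 45 g but contradicts the regimen.
- The 50 mL can also mentioned in Protocol 4.7: not the presentation used in this study.

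**The case against.** The strongest reply is that the flow rate, not the 45 g, is the wrong figure. It appears once, in a packaging description, with no tolerance. The SAP works from a single starting weight per patient, and Protocol 8.4.1 has the patient return one container. At 0.8 mL/s a 150 mL can covers 30 days only for puffs up to 150 / (120 x 0.8) = 1.56 s, so part of the permitted range could not be supplied. At 0.375 g per puff it could. On this reading the compliance percentages are sound and the error is a protocol sentence that no analysis uses. The argument is reasonable, but it is inference. Neither document says where 154.5 g comes from or states a delivered dose per puff.

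A second reply is that the error would show itself: Table 14.3.1.2 prints quartiles and extremes, and values above 200% would be noticed. That holds for patients who were adherent. A value near 100% stays ambiguous, because it fits either full use at 0.375 g per puff or about half use at 0.8 mL/s with 1 s puffs.

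Third, no result moves. Compliance is descriptive, secondary efficacy uses the FAS, and no listed table uses the Per Protocol Set. Treatment non-compliance is a major deviation (SAP 7.2), but neither document sets a percentage cut-off. Returned-can weight is summarised in Table 14.2.4, so grams used can be recovered. All of this stands and limits the importance of the point. It does not make the percentage interpretable.

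**Conclusion.** The inconsistency is real. The stated flow rate, the stated puff length and the 45 g cannot all be right, and the gap is at least a factor of 96 / 45 = 2.1. The only outside assumption is a density of at least 1.00 g/mL; a higher density widens the gap.

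The direction is not settled by the documents. The statement that 100% means at most about 47% of the regimen is conditional on the 0.8 mL/s rate. If 45 g is right instead, the percentages stand and the protocol's flow rate or puff duration is overstated at least twofold. Either way one document needs correcting before Table 14.3.1.2 can be read. This should be fixed, but it does not threaten the efficacy or safety analyses.

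**What to change.** Before database lock, or before Table 14.3.1.2 is produced if the database is already locked, obtain grams per puff from the manufacturer, or weigh a can before and after a fixed number of 1 s and 2 s puffs. Then define theoretical quantity (g) = verified grams per puff x 4 puffs/day x 30 days, and cite the source in SAP section 9.

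- If 0.8 mL/s and 1 s are confirmed, use 96 g as the minimum. The theoretical final weight becomes 199.5 - 97.9 = 101.6 g to 199.5 - 96 = 103.5 g, instead of 154.5 g. State that the 2 s end is capped by the 150 mL can.
- If 45 g is confirmed, keep it and state that the 8 mL per 10 s or the 1-2 s figure does not describe actual delivery.

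In either case, make the printed subtraction agree with the 30-day weight. Scaling to each subject's actual treatment days is optional and needs a recorded stop date.

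The cost is one manufacturer query or a short bench weighing, and then one constant or one explanatory sentence. The returned-can weights already planned are enough, so no new patient data are needed. If the 0.8 mL/s rate is confirmed, reported compliance falls by at least half (45 / 96 = 0.47 of its former value).
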